#### **Abstract**

The purpose of this study is to examine the human thermoregulatory impact of applying a commercially available menthol gel (BioFreeze) to the skin prior to moderate intensity walking under heated conditions. Eligible participants will be aged 19-45 years, have no previously known adverse reactions to menthol (active ingredient in BioFreeze) based upon a self-report, no adverse reactions to BioFreeze as determined through gel application to a small forearm area, and cleared for physical activity via the 2022 Physical Activity Readiness Questionnaire (PARQ). There will be a total of 3 experimental visits to the laboratory. Visit 1 will test for adverse BioFreeze reaction by applying a small amount of gel to the forearm (~2 x 2 in). Anthropometric and body composition data will also be collected at this time. Visits 2 and 3 will consist of 30 min of treadmill walking at a moderate pace (3.5 mph, 5% grade) under hot conditions (38°C, 60%RH). Visits 2 and 3 will be randomized and counterbalanced for BioFreeze or a hypoallergenic gel (control) application. Gels will be applied to areas commonly exposed during outdoor activity in warm conditions (shoulder to wrist, mid-thigh to ankle). Accordingly, participants will wear shorts and a tank top shirt during exercise. Core temperature, skin temperature, galvanic skin response, laser doppler blood flow, and heart rate will be continuously recorded throughout the exercise bout via an integrated analog to digital converter. Sweat will be collected during exercise using commercially available absorbent patches. Thermal sensation will be assessed throughout exercise via the ASHRAE thermal sensation likert scale (cold to hot). Lastly, nude body weight will be recorded pre and post exercise for sweat rate determination. The BioFreeze and control trials will be separated by a 7 to 14 day washout period.

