# Purpose and Rationale

The purpose of this study is to examine the impact of applying a menthol-based gel to the skin on human thermoregulation and thermal perception during exercise in the heat.

Transient receptor potential (TRP) channels are a family of membrane proteins evolved to interpret environmental stimuli through ion channels. One of these channels, the TRP melastatin 8 (TRPM8), is responsible for the sensation of innocuous cool temperatures and it might be responsible for noxious cold temperatures [1,2]. When applied topically, menthol acts upon a cold transduction enzyme to decrease the thermal sensitivity of TRPM8. This decreased thermal sensitivity allows activation of TRPM8 at warmer temperatures, mimicking a cool sensation in warm environments. This cool menthol feeling is used widely in everyday commercial products, but most popular when used as an analgesic in medicated pain-relieving gels/creams.

Current recommendations suggest menthol can be used as an ergogenic aid resulting in an improved performance within heated environments [1]. By decreasing thermal sensitivity of TRPM8 receptors, menthol exerts a physiological response that is perceived as external cooling. The most salient response is an increase in heat conservation, resulting in a reduced exercise capacity due to fatigue associated with a rise in core body temperature [3]. It seems

the application and concentration strength of menthol application to the skin may be the most obvious influential factors. As such, researchers have used proprietary menthol solutions with varying intensities (0.05- 10%) [1], yet, to our knowledge, no one has investigated widely available, over-the- counter products. Indeed, the translation from proprietary formula to over-the-counter application is unknown. Furthermore, it is unclear if currently available menthol products may also aid in performance. This incongruence requires further investigation into the effect of menthol on exercise performance.

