#### Research Plan

Three experimental visits to the laboratory will be conducted. All visits will take place at the University of Nebraska at Omaha, Exercise Physiology Laboratory. Visit 1 will consist of the physical activity readiness questionnaire (PARQ), adverse reaction to BioFreeze, and body composition (hydrostatic weigh, bioelectrical impedance). Visits 2 and 3 will be separated by 7-14 days, randomized, and counterbalanced for experimental (BioFreeze) and control (hypoallergenic cream) trials. Both the experimental and control visits will follow the same protocol.

Participants will arrive following an overnight fast state while also refraining from strenuous activity, alcohol consumption, tobacco use, and recreational drugs for the previous 24-hour period. During these visit researchers will apply BioFreeze using a gloved hand from shoulder to wrist and mid-thigh to ankle (areas outside of the clothing). A hypoallergenic cream will be applied during the control visit.

Exercise will consist of 30 min of moderate intensity treadmill walking (3.5 mph at 5% grade) within a heated temperature/humidity-controlled chamber (38°C, 60% relative humidity).

Participants will be weighed before, and after completion of the exercise calculate sweat rate. Prior to the exercise session, participants will sit for 5 min in an ambient room temperature environment as a baseline. During baseline and during the exercise core temperature, skin temperature, laser doppler blood flow, galvanic skin response, and heart rate will be collected continuously. Sweat patches will be adhered to the forehead during exercise at minute 10 for collection of sweat composition over the next 10-20 minutes.

Thermal perception using the ASHRAE scale (cold to hot) will be assessed pre and during exercise.

### VISIT 1

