Visit 1 will take approximately 1 hour. Informed consent will be given. Participants will then complete the physical activity readiness questionnaire (PARQ) to be cleared for physical activity. Participants will have a small amount of the BioFreeze cream applied to a small area of the forearm (~2 x 2 in) to test for any adverse reaction over a period of 15 minutes. This initial skin reaction test is not a part of the research protocol. Then, resting blood pressure will be taken. Those without a reaction, and a resting blood pressure lower than 140/90, will have height, weight, and body fat composition measured. Height and weight will be measured using a medical scale and stadiometer, respectively. Body fat will be assessed with hydrostatic weighing using an electronic load cell-based system (Exertech, Dresbach, MN) correcting for residual lung volume or via a bio-electrical impedance analyzer (InBodyUSA, Cerritos, CA).

## VISITS 2 AND 3

Visits 2 and 3 will take approximately 2 hours each. Upon arrival at the lab, a nude body weight will be collected with the subject in a private room. While still in the room, subjects will self-insert a rectal thermistor 12-15 cm beyond the anal sphincter and don a chest strap heart rate monitor. After dressing in their exercise clothing, subjects will exit the private room so that chest, forearm, and calf thermistors can be adhered to the skin with tape.

Laser doppler flow (forearm and or/finger) will be adhered with tape and galvanic skin response (fingers) will be adhered using Velcro straps to the skin. Measuring instruments will be recorded using an integrated digital to analog converter (ADInstruments, Colorado Springs, CO).

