Following instrumentation, subjects will sit for 5 minutes as a baseline in a temperate environment. Immediately after, a researcher with gloved hands will topically apply BioFreeze or the control hypoallergenic cream from the shoulder to wrist and mid-thigh to ankle. Subjects will then enter the heat chamber (38°C, 60% relative humidity) and immediately begin a 30-minute walk on a treadmill (3.5 mph, 5% grade). Subjects will be intermittently asked to hold their arm steady for laser doppler flow collection (10, 20, 30 minutes). Subjects will also briefly pause at minute 10 in order to adhere an absorbent patch to their forehead for sweat collection over the following 10-20 minutes. Thermal perception using the ASHRAE scale (cold to hot) will be assessed pre and during exercise. After 30 minutes of walking, subjects will exit the chamber for removal of all skin and finger sensors. Subjects will then reenter the private room, remove their own rectal thermistor with gloved hands, and then a final nude body weight will be recorded after toweling off.

The rectal thermistor will measure core temperature. The heart rate monitor will measure the beats of the heart. Skin thermistors will measure the temperature of the skin surfaces. Laser doppler flow measure the relative units of blood flow velocity.

Galvanic skin response measures skin conductivity changes as individuals begin to sweat. Sweat is collected for assessment of sweat composition. Thermal perception is assessed for individual perception surrounding the temperature of the ambient environment. Nude body weight is measured to calculate sweat rate.

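### The control is a gel in the Abstract and a cream in the Research Plan, and nothing says its base matches BioFreeze, so a base effect could be mixed with the menthol effect

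*Combined protocol and SAP*

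**What the plan says.** The Abstract defines the comparison thus: "Visits 2 and 3 will be randomized and counterbalanced for BioFreeze or a hypoallergenic gel (control) application". It uses one plural noun for both products: "Gels will be applied to areas commonly exposed during outdoor activity in warm conditions".

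The Research Plan describes the control differently: "A hypoallergenic cream will be applied during the control visit". Under Visits 2 and 3, the researcher is to "topically apply BioFreeze or the control hypoallergenic cream from the shoulder to wrist and mid-thigh to ankle".

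BioFreeze is described just as loosely. The Abstract's purpose concerns "applying a commercially available menthol gel (BioFreeze) to the skin prior to moderate intensity walking under heated conditions", and its account of the forearm reaction test also speaks of gel. The Visit 1 text describes the same test as follows: "Participants will have a small amount of the BioFreeze cream applied to a small area of the forearm".

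The control is not identified by product, composition or amount applied. Nothing says whether it is BioFreeze's base without the menthol, or close to it.

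**The concern.** The Purpose and Rationale section argues from the ingredient. It describes menthol's action on TRPM8, states that "menthol exerts a physiological response that is perceived as external cooling", and closes by calling for work on what menthol does to exercise performance. To attribute a difference to menthol, the control should differ from BioFreeze in menthol and in as little else as possible.

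A laboratory could comply with the Research Plan by using any hypoallergenic cream. If that cream's base evaporates, covers the skin or leaves residue differently from the BioFreeze base, the difference goes with the treatment in every participant. It could imitate a menthol effect, enlarge it or hide it. Randomised order and the 7 to 14 day washout deal with period effects and carry-over. They do not touch a difference between the two products themselves.

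**Working it through.** **1. The plan's own figure.** Statistical Analysis, Recruitment gives an SD of paired differences of 0.86, a true mean difference of 0.75, 12 trials per condition, power 0.8 and type I error 0.05. Sidedness is not stated; two-sided is assumed.

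- Normal approximation: n = ((1.960 + 0.842) × 0.86 / 0.75)² = 10.32, rounded up to 11.
- Paired t test with noncentrality (0.75 / 0.86)√n = 0.872√n: power is 0.785 at n = 12 and 0.823 at n = 13.

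The stated 12 is reproduced to within one participant. Nothing in this point changes it.

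**2. The wording side by side.**

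- Control: a gel in the Abstract; a cream in the Research Plan overview and under Visits 2 and 3.
- BioFreeze: a gel in the Abstract; a cream under Visit 1.
- Both together: gels in the Abstract.

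Three readings fit. If the two words are used interchangeably, no mismatch is established, but the control is still unidentified. If the Research Plan is read literally throughout, both products are creams. If the Research Plan governs the control and the Abstract governs BioFreeze, a cream is compared with a gel. The text does not settle which is meant, and under none of the three is the base stated to match.

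**3. Which measurements a base could reach.**

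- *Timing.* Product goes on after the 5-minute baseline and just before the participant enters the chamber. Any base effect falls in the measured period, and the baseline cannot remove it.
- *Skin temperature.* Two of the three skin sites, forearm and calf, lie in the treated region (shoulder to wrist, mid-thigh to ankle).
- *Skin blood flow.* Laser Doppler is on the forearm and/or finger, so it may be in the treated region.
- *Sweat rate.* The first nude weight (W1) is taken on arrival, before application. The last (W2) is taken after exercise and toweling. With S the sweat lost and R the product left on the skin, W2 = W1 − S + R, so the recorded loss is W1 − W2 = S − R (other mass losses ignored). A difference in R between products passes gram for gram into the difference in sweat loss.
- *Thermal sensation.* A base that evaporates or occludes could itself change how warm the skin feels.

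**4. Why two conditions cannot separate the parts.** Let M be the menthol effect and V the effect of each base, taken as additive. The expected paired difference is M + (V_BioFreeze − V_control). That is one contrast with two unknowns. It equals M only if the bases act alike.

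**5. Illustration on assumed values.** The documents give no base effect, so this shows only how a difference would behave if it existed. Set M = 0, keep SD 0.86 and n = 12, and use a two-sided paired t test at 0.05:

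- base difference 0: probability of significance 0.05
- 0.25: 0.15
- 0.50: 0.45
- 0.75: 0.79

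The units are those of the plan's 0.75, which it does not name. The planned analysis is a time-by-condition ANOVA, so the paired test is a simplification.

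**The case against.** The strongest reply is that the two words are used loosely. The forearm test is done with gel in the Abstract and with cream under Visit 1, and the Abstract calls both products gels. A reader might infer that a gel is certainly being compared with a cream and that the trial is therefore confounded. The documents do not support that, because a mismatch in product form is possible but not shown. This part of the reply stands.

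The second reply is that the stated purpose, in the Abstract and at the start of Purpose and Rationale, concerns a commercial product, and the gap identified is the lack of work on over-the-counter products. A randomised crossover of BioFreeze against a topical control can answer that. A reader might infer that the comparison fails altogether; it does not. Only the ingredient-level reading depends on the base. But the rationale does invite that reading, so the limit needs stating.

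The third reply is that no bias has been measured. This also stands. A reader might try to put a temperature on it from the heat removed by an evaporating base. That needs the mass applied, the volatile fraction of each base, the share of latent heat drawn from the body in a 38°C chamber, and how far evaporating base displaces sweat evaporation. None is given, and with equal volatile content the difference would be zero.

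What the replies do not answer is that, even if the words are interchangeable, the plan does not say what the control is or whether it is matched.

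**Conclusion.** The point holds in conditional form. The contradiction over the control is plain on the page, and so is the absence of any statement that its base matches BioFreeze. If the control is a cream with a different base, a menthol effect and a base effect would be inseparable for limb skin temperature, weight-based sweat rate and thermal sensation, and for skin blood flow where the forearm is used. Whether the bases differ is unknown, and the size and direction of any effect cannot be derived from the documents. The probabilities in the illustration rest on assumed differences and are not estimates of bias. The comparison of BioFreeze with the control actually used remains valid, and the sample size is unaffected. The point merits a change because the risk bears on several outcomes and is cheap to reduce.

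**What to change.** Reconcile the Abstract, the Research Plan overview, Visit 1 and Visits 2 and 3 so that each product has one description throughout. Name the control and give its base. Choose a menthol-free gel whose base is as close as practicable to that of BioFreeze, and apply it over the same area in the same way. State in the plan how close the match is.

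If an unmatched cream is kept, say in the purpose and the conclusions that the contrast is BioFreeze versus that named product, and do not ascribe differences to menthol.

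The cost is a correction of wording in four places and possibly a different inexpensive product. No visits, staff or participants are added. The downside is that the match will be approximate, so some base difference may remain and should be acknowledged when results are interpreted.

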### **Participants**

12-15 subjects, age 19 to 45 years, will be needed to complete the study. Nineteen is the age of majority at the study site. The 2022 physical activity readiness questionnaire (PARQ) requires that adults aged >45 who are not accustomed to regular physical activity seek professional consultation prior to beginning physical activity. Thereby, keeping an age range of 19-45 ensures that the participants will be of consenting age and cleared for physical activity participation.

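### The 7-14 day gap between gel visits often changes cycle phase in naturally menstruating participants; same-phase booking and baseline adjustment would cheaply remove avoidable within-person noise in core temperature.

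*Combined protocol and SAP*

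**What the plan says.** The interval is given twice. The Abstract says "The BioFreeze and control trials will be separated by a 7 to 14 day washout period"; the Research Plan says "Visits 2 and 3 will be separated by 7-14 days, randomized, and counterbalanced for experimental (BioFreeze) and control (hypoallergenic cream) trials".

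The Participants section says "12-15 subjects, age 19 to 45 years, will be needed to complete the study". The other entry conditions are PARQ clearance, resting blood pressure and absence of a skin or known menthol reaction. Sex is not restricted.

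The Research Plan standardises the participant's state before each visit: "Participants will arrive following an overnight fast state while also refraining from strenuous activity, alcohol consumption, tobacco use, and recreational drugs", with the abstentions covering 24 hours. Menstrual phase and hormonal contraception appear nowhere in eligibility, scheduling, pre-visit control, data collection or analysis.

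On measurement, "The rectal thermistor will measure core temperature", recorded continuously at baseline and during exercise. At each gel visit, "Following instrumentation, subjects will sit for 5 minutes as a baseline in a temperate environment"; the gel goes on after that.

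Statistical Analysis (Interventions) specifies a two-way repeated-measures ANOVA, time by condition, for the dependent variables. It has no phase, sex, period or sequence term. It does not say whether absolute values or changes from baseline are analysed.

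**The concern.** A crossover compares each participant with herself and works best when little but the gel differs between visits. The plan takes care over this for food, activity, alcohol, tobacco and drugs. For a naturally menstruating participant, however, 7-14 days is a quarter to a half of a 28-day cycle, so the interval itself tends to move her into the other phase.

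If core temperature differs between phases (an assumption here; the documents give no figure), that difference enters her paired contrast. Its sign depends on which phase she was in at visit 2 and which gel came first, so a period term would not remove it. What is at stake is precision on a central thermoregulatory outcome in a trial of 12-15 people with no spare power at 12.

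**Working it through.** **Step 1. Reproduce the planned sample size.** Inputs from Statistical Analysis (Recruitment): SD of paired differences 0.86, mean difference 0.75, power 0.8, alpha 0.05. Two-sided testing is assumed, since the null is a zero difference.
- Normal approximation: n = (0.86 × (1.960 + 0.842) / 0.75)² = 10.3, so 11.
- Noncentral t, paired: power is 0.785 at n = 12 and 0.823 at n = 13.

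The stated 12 is reproduced closely enough. The baseline for what follows is 0.785.

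**Step 2. How often the phase changes.** For gap g, cycle length C, luteal length L and a random start day, P(different phase) = 2 × min(g, L, C − L, C − g) / C. With C = 28 and L = 14 (assumed):
- g = 7: 14/28 = 50%
- g = 10: 20/28 = 71%
- g = 14: 28/28 = 100%
- Mean over gaps 7 to 14: 2 × (84/8) / 28 = 75%

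With cycles of 24-35 days and luteal phases of 10-14 days, the mean is 53-81%; at exactly 7 days it is 40-58%.

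**Step 3. Bias or noise.** Simulation with order split 6/6 (the ratio is not stated; 1:1 assumed), n = 12: the mean contribution of the shift to the gel-minus-control contrast is about 0 (within about 0.001 °C), and type I error is 0.047-0.053. It is noise.

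**Step 4. Size of the noise in absolute values.** Let f be the share cycling, q the share changing phase, d the shift and s the paired SD without it. Then SD′ = √(s² + f·q·d²). Assumed: f = 6/12, q = 0.75, so f·q = 0.375; d = 0.3 °C (range 0.2-0.5). The effect is held at the plan's ratio, 0.75/0.86 = 0.872 SD. Power is for the paired contrast at n = 12, by simulation; the ranges run from d = 0.2 to d = 0.5.

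| s (°C) | SD′ at d = 0.3 (range) | Power at d = 0.3 (range) |
|---|---|---|
| 0.20 | √(0.04 + 0.03375) = 0.272 (0.235-0.366) | 0.52 (0.65-0.31) |
| 0.30 | √(0.09 + 0.03375) = 0.352 (0.324-0.429) | 0.65 (0.72-0.48) |
| 0.86 | √(0.7396 + 0.03375) = 0.879 (0.869-0.913) | 0.77 (0.78-0.74) |

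Putting SD′ into the noncentral t gives nearly the same values (0.53, range 0.65-0.33, in the first row). With f = 0, power stays at 0.785. With 15 participants, 6 of them cycling, and d = 0.3, power is 0.68 (s = 0.2) or 0.79 (s = 0.3), against 0.88 with none.

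**Step 5. Chance imbalance against the effect.** The SD of the shift's contribution to the mean contrast is √(0.375 × 0.09 / 12) = 0.053 °C (0.035-0.088 for d = 0.2-0.5). The assumed effect is 0.872 × 0.20 = 0.17 °C or 0.872 × 0.30 = 0.26 °C. At d = 0.3 the imbalance is therefore about 20-30% of the effect.

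**Step 6. Which contrasts are exposed.** Write a participant's temperature at time t in a visit as response(t) plus a phase offset d. In the change from the pre-gel baseline, (response(t) + d) − (response(0) + d), the offset drops out. The Time x condition interaction is built from such differences, so it drops out there too. It stays in the condition main effect on absolute values. A phase difference in the rise during exercise would survive in all three; the documents give nothing from which to size it.

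**The case against.** The strongest reply is that the design already supplies the remedy. A pre-gel baseline is recorded at each visit and the ANOVA includes the Time x condition term, so a constant offset does not touch that test, and the power losses in the table do not describe it. This stands. It does not dispose of the point, because the same ANOVA also tests condition on whatever scale is entered, and the plan does not say that this is change from baseline.

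The second reply is that the size is imported: the shift, the smaller paired SDs and the number cycling are not in the documents. This stands as well, which is why the result is a range that includes nearly nothing (0.785 to 0.77) and zero. The 0.86 has no outcome or unit, and may already contain visit-to-visit variation of this kind. It can neither confirm the larger losses nor show that core temperature is protected.

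Three stronger readings are tempting and not supported:
- A reader might infer that the gel effect is biased. Randomised, counterbalanced order rules that out in expectation.
- A reader might infer that a chance imbalance could be as large as the gel effect. Under the same assumptions it is typically a fifth to a third of it, and about half at the most extreme (0.088 against 0.17 °C).
- A reader might infer that most cycling participants will certainly change phase. That is an average over gaps; if visits cluster at 7 days it is about half.

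Sweating and skin blood flow may also vary with phase, but the documents provide no basis for a figure, so no claim is made for them.

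**Conclusion.** The point holds as a cheap improvement, not as a flaw that threatens validity. The 7-14 day window places half to all of naturally menstruating participants in different phases at the two gel visits (75% on average under a 28-day cycle), and the plan neither controls nor records it. The consequence is extra within-person noise in absolute core temperature, with no bias and no inflation of type I error. Depending on the true paired SD, the loss of power runs from about two points to more than a quarter of the scale at a 0.3 °C shift with half of 12 participants cycling (0.785 to 0.77, or to 0.52). It is nil if no naturally cycling participants enrol, and nil for the interaction or change from baseline if the shift is constant within a visit.

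**What to change.** 1. **Abstract and Research Plan:** state that naturally menstruating participants have both gel visits in the same self-reported cycle phase, within the existing 7-14 day window. For example, visit 2 falls in the first days after onset of bleeding and visit 3 seven or eight days later. A start on days 1-4 puts visit 3 on days 8-12, before mid-cycle in a 28-day cycle; shorter cycles need the earlier end of that range. Scheduling for everyone else is unchanged.
2. **Research Plan (Visits 2 and 3):** record cycle day and hormonal contraceptive use at each visit, so that phase can be described and examined. It cannot be reconstructed reliably afterwards.
3. **Statistical Analysis (Interventions):** state that core temperature is analysed as change from, or adjusted for, the pre-gel baseline of the same visit. This removes a constant offset even where same-phase booking fails.

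Cost: a short amendment and a brief self-report item at each visit, with no new procedures or staff. The downsides are less flexible booking for some participants and reliance on self-reported phase.
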